## **6 STUDY TREATMENTS**

Study treatment is defined as any investigational treatment, marketed product, placebo, or medical device intended to be administered to a study participant according to the study protocol.

### **6.1 Treatments administered**

Eligible study participants will be randomized in a 2:2:2:1 ratio as noted in the Study Schema (Figure 1-1).

A summary of the treatments administered is provided in Table 6-1.

**Table 6-1: Study medications administered**

ARM Name	Bimekizumab	Placebo
Intervention name	Bimekizumab	Placebo
Type	Biologic	Drug
Dose formulation	Solution for injection (pre-filled 1-mL syringe)	Solution for injection (pre-filled 1-mL syringe)
Unit dose strengths	160mg/mL	0.9% sodium chloride aqueous solution (physiological saline, preservative free) of US Pharmacopoeia/European Pharmacopoeia quality appropriate for injection; same volume to maintain blinding to the study participant
Dosage levels	320mg	Not applicable
Route of administration	Subcutaneous injection	Subcutaneous injection
Use	Experimental	Placebo comparator
Investigational Medicinal Product and Non-Investigational Medicinal Product	Investigational Medicinal Product	Investigational Medicinal Product
Sourcing	Provided centrally by the Sponsor.	Provided centrally by the Sponsor.
Packaging and labeling	Study Intervention will be provided in a kit. Each kit will be labeled as required per country requirement	Study Intervention will be provided in a kit. Each kit will be labeled as required per country requirement
Current/Former names or aliases	Bimekizumab	Not applicable

Because of differences in the dosing schedules and in order to maintain blinding, all study participants will receive 2 injections sc every 2 weeks from Week 0 to Week 46 as depicted in [Table 6-2](#).

**Table 6–2: Dosing scheme**

Week Dose Assignment	Initial Treatment Period (weeks after first dose)												Maintenance Treatment Period (weeks after first dose)											
	Baseline 0	2	4	6	8	10	12	14	16	18	20	22	24	26	28	30	32	34	36	38	40	42	44	46
Bimekizumab 320mg Q2W/Q2W	••	●	●	●	●	●	●	●	●	●	●	●	●	●	●	●	●	●	●	●	●	●	●	●
Bimekizumab 320mg Q4W/Q4W	••	○	●	○	●	○	●	○	●	○	●	○	●	○	●	○	●	○	●	○	●	○	●	○
Bimekizumab 320mg Q2W/320mg Q4W	••	●	●	●	●	●	●	●	●	○	●	○	●	○	●	○	●	●	●	●	●	●	●	○
Placebo/bimekizumab 320mg Q2W	○○	○	○	○	○	○	○	○	○	○	○	○	○	○	○	○	○	○	○	○	○	○	○	○

Q2W=every 2 weeks; Q4W=every 4 weeks

Notes: A bimekizumab 160mg injection is depicted by a black circle (●). A placebo injection is depicted by a white circle (○).

## **6.2 Preparation, handling, storage, and accountability requirements**

The Investigator or designee must confirm appropriate temperature conditions have been maintained during transit for all study treatment received and any discrepancies are reported and resolved before use of the study treatment.

Only study participants enrolled in the study may receive study treatment and only authorized site staff may supply or administer study treatment. All study treatments must be stored in a secure, environmentally controlled, and monitored (manual or automated) area in accordance with the labeled storage conditions with access limited to the Investigator and authorized site staff.

The Investigator, institution, or the head of the medical institution (where applicable) is responsible for study treatment accountability, reconciliation, and record maintenance (ie, receipt, reconciliation, and final disposition records).

In case an out-of-range temperature is noted, it must be immediately reported as per instructions contained in the IMP Handling Manual.

Further guidance and information for the final disposition of unused study treatment are provided in the IMP Handling Manual.

### **6.2.1 Drug accountability**

A Drug Accountability form will be used to record IMP dispensing and return information on a by-participant basis and will serve as source documentation during the course of the study. Details of any IMP lost, damaged (due to breakage or wastage), not used, partially used, disposed of at the study site, or returned to the Sponsor or designee must also be recorded on the appropriate forms. All supplies and pharmacy documentation must be made available throughout the study for UCB (or designee) to review.

The Investigator (or designee) is responsible for retaining all used, unused, and partially used containers of IMP until returned or destroyed.

The Investigator may assign some of the Investigator's duties for drug accountability at the study site to an appropriate pharmacist/designee.

The Investigator must ensure that the IMP is used only in accordance with the protocol.

Periodically, and/or after completion of the clinical phase of the study, all used (including empty containers)/partially used, unused, damaged, and/or expired IMP must be reconciled and either destroyed at the site according to local laws, regulations, and UCB standard operating procedures or returned to UCB (or designee). Investigational medicinal product intended for the study cannot be used for any other purpose than that described in this protocol.

## **6.3 Measures to minimize bias: randomization and blinding**

### **6.3.1 Randomization and numbering of participants**

An interactive response technology (IRT) system will be used for assigning eligible study participants to a treatment regimen (as applicable) based on a predetermined production randomization and/or packaging schedule provided by UCB (or designee). The randomization schedule will be produced by the IRT vendor. The IRT will generate individual assignments for kits of IMP, as appropriate, according to the visit schedule.

To enroll a study participant at Screening, the Investigator or designee will contact the IRT and provide brief details about the study participant to be enrolled. Each study participant will receive a unique number assigned at Screening that serves as the study participant identifier throughout the study. The study participant number will be required in all communication between the Investigator or designee and the IRT regarding a particular study participant. Study participant numbers and kit numbers will be tracked via the IRT.

To randomize a study participant, the Investigator or designee will contact the IRT and provide brief details about the study participant to be randomized. The IRT will automatically inform the Investigator or designee of the study participant's randomization number. The IRT will allocate kit numbers to the study participant based on the study participant number during the course of the study. The randomization number must be incorporated into the case report form (CRF).

### **6.3.2 Procedures for maintaining and breaking the treatment blind**

#### **6.3.2.1 Maintenance of study treatment blind**

All study participant treatment details will be allocated and maintained by the IRT system.

The IRT provider will receive the randomization code at the start of the study.

Due to differences in presentation between bimekizumab and placebo treatments, special precautions will be taken to ensure study blinding; study sites will have blinded and unblinded personnel. Bimekizumab and placebo injections will be administered at the investigational sites by unblinded, dedicated study personnel according to the site-specific blinding plan. Unblinded study personnel will be responsible for recording the administration information on source documents, and administration of the IMP as sc injections. Study site pharmacists or other suitably qualified site personnel who are responsible for preparation and administration of IMP treatments will have access to treatment allocations for individual study participants via the IRT. The unblinded pharmacy monitors from the Contract Research Organization (CRO), and the UCB Clinical Trial Supply representative will also have access to the treatment allocations and to the drug accountability records, if applicable.

The following individuals may, as necessary, have access to the randomization code as indicated:

- Members of the Data Monitoring Committee (DMC) who participate in unblinded sessions will be given information about the IMP allocation for those study participants for whom data are provided.
- The unblinded, independent CRO staff supporting preparation of the data outputs for the DMC reviews.

The unblinded study site personnel will not be involved in the study in any way other than assuring the IMP is taken from the correct kit and prepared according to the IMP-handling manual, and administering the IMP to the study participants.

In addition, high-sensitivity C-reactive protein (hs-CRP) results will not be reported to any blinded study personnel as long as the study remains blinded.

#### **6.3.2.2 Breaking the treatment blind in an emergency situation**

In the event of an emergency, it will be possible to determine to which treatment arm and dose the study participant has been allocated by contacting the IRT. The Investigator is responsible for

breaking the treatment blind in case of emergency. All sites will be provided with details of how to contact the system for code breaking at the start of the study. The Medical Monitor and/or UCB study physician or equivalent should be consulted prior to unblinding, whenever possible.

The Clinical Project Manager will be informed immediately via the IRT when a code is broken, but will remain blinded to specific treatment information. Any unblinding of the IMP performed by the Investigator must be recorded in the source documents and on the Study Termination electronic CRF (eCRF) page.

Inadvertent unblinding will be listed as a major protocol deviation.

#### **6.4 Treatment compliance**

During the double-blind Initial Treatment and Maintenance Treatment Periods, IMP will be administered in the clinic and compliance will be recorded at the visit by study personnel in the eCRF. Drug accountability must be recorded on the Drug Accountability form.

#### **6.5 Concomitant medications/treatments**

##### **6.5.1 Permitted concomitant treatments (medications and therapies)**

The following concomitant medications are permitted during the study:

- Wound care: Concomitant use of wound care dressings on HS wounds is allowed; however, options are limited to alginates, hydrocolloids, and hydrogels and use of these will be recorded in the eCRF.
- Lesion care: Concomitant use of saline, water, and/or Vaseline (petroleum jelly) is allowed for care of skin lesions and use of these will be recorded in the eCRF.
- Analgesic therapy:
  - Study participants will be required to wash out of all analgesics for HS-related pain 14 days prior to Baseline. However, if a study participant is on a stable (scheduled) dose of a non-opioid analgesic for HS-related pain, or for a non-HS medical condition (eg, osteoarthritis, neuropathic pain), the study participant may continue the analgesic. Opioid analgesics (including tramadol) are excluded for any indication.

Notes: (1) Dose should be stable for 14 days prior to Baseline, and is anticipated to remain stable throughout study participation. (2) Dosing PRN is not considered stable, but (for example) taking an NSAID 2 or 3 times per week every week is considered a stable dose.

- If a study participant's pain (HS-related or non-HS-related) worsens after Baseline, the study participant may initiate analgesic therapy at any time and/or per local labeling as follows: For HS-related pain, permitted analgesics are limited to ibuprofen at a dose of up to 800mg orally every 6 hours, not to exceed 3.2g/24 hours; and/or acetaminophen/paracetamol as per local labeling. For non-HS-related pain, initiation of any new analgesic/treatment must not include exclusionary medications (eg, opioids and tramadol), and must be recorded on the eCRF.
- All analgesic use (start dates, end dates, dose, reason) will be recorded on the eCRF.

- Antibiotic therapy:

- For study participants entering the study in the antibiotic strata, they should be on a stable dose and regimen of doxycycline, minocycline, or an equivalent systemic tetracycline for 28 days prior to Baseline (Visit 2). The dose and regimen should remain stable throughout study participation, but at least through Week 16. Antibiotics taken on a PRN basis are not considered as a stable dose. After Week 16, participants may receive an antibiotic if required in the judgement of the Investigator. Also see Section 6.5.3.1 for details on systemic antibiotic rescue medication.
- All antibiotic use (start dates, end dates, dose, reason) will be recorded on the eCRE.

### **6.5.2 Prohibited concomitant treatments (medications and therapies)**

The following concomitant medications and therapies are prohibited during the study (also see Table 6–3):

- All biologic therapy with a potential therapeutic impact on the disease being studied, including those listed in Table 6–3.
- Phototherapy (psoralen and ultraviolet A and/or ultraviolet B) or photochemotherapy.
- Immunomodulatory therapy, including topical or systemic steroids except as noted in Section 6.5.3.1 (Rescue Medications/Lesion Intervention), and Table 6–3.
- Topical and systemic therapies for HS (see Table 6–3).
- Surgical or laser intervention for an HS lesion except as outlined in Section 6.5.3.1 (Rescue Medications/Lesion Intervention).

**Table 6–3: Exclusions for prior medications**

Drug class	Exclusion criteria
Systemic antibiotics	Used within 2 weeks prior to the Baseline Visit. Note: See exception for permitted, stable doses of antibiotics in Section 6.5.1.
Systemic retinoids	Used within 4 weeks prior to the Baseline Visit
Systemic treatment (non-biologic) 

• Apremilast

• Systemic immunosuppressant agents (eg: methotrexate, cyclosporine, azathioprine, thioguanine)

• Systemic fumarate

• Systemic oral or injectable corticosteroids

• Phototherapy and radiotherapy (eg, psoralen and ultraviolet A and/or ultraviolet B) or photoradio/chemotherapy

	Used within 4 weeks prior to the Baseline Visit. Note: See exception for permitted, stable doses of antibiotics in Section 6.5.1.
Anti-tumor necrosis factors (including biosimilars) adalimumab, etanercept, certolizumab, golimumab, infliximab	Used within 12 weeks prior to the Baseline Visit. Note: For etanercept, used within 1 month prior to the Baseline Visit.
Other biologics Abatacept Anakinra Natalizumab Belimumab Tocilizumab Efalizumab Or other biologics approved by regulatory agencies after the protocol is approved	Used within 12 weeks prior to the Baseline Visit Note: for other biologics approved by regulatory agencies after the protocol is approved: Washout of 6 months prior to the Baseline Visit or 5 half-lives prior to the Baseline Visit, whichever is greater.
Secukinumab, brodalumab, ixekizumab and other IL-17 inhibitors approved by regulatory agencies after the protocol is approved	Washout of 6 months prior to the Baseline Visit or 5 half-lives prior to the Baseline Visit, whichever is greater.
IL-12, IL-23 inhibitors: Ustekinumab Risankizumab Tildrakizumab Guselkumab Or other biologics approved by regulatory agencies after the protocol is approved	Used within 6 months prior to the Baseline Visit Note: for other biologics approved by regulatory agencies after the protocol is approved: Washout of 6 months prior to the Baseline Visit or 5 half-lives prior to the Baseline Visit, whichever is greater.

**Table 6–3: Exclusions for prior medications**

Drug class	Exclusion criteria
Janus kinase inhibitors Tofacitinib Baricitinib Filgotinib Upadacitinib Or other janus kinase inhibitors approved by regulatory agencies after the protocol is approved	Used within 12 weeks of the Baseline Visit or 5 half-lives prior to the Baseline Visit, whichever is greater
Any other systemic HS drug under investigation (or approved after the protocol is approved)	Used within 12 weeks or 5 half-lives prior to the Baseline Visit, whichever is greater
Rituximab	Used within 2 years of the Baseline Visit
Topical drugs for HS (including intralesional corticosteroids, over-the-counter and prescription drugs, as well as disinfectants for skin lesions, eg, chlorhexidine, povidone iodine)	Used within 14 days of the Baseline Visit
Topical corticosteroids (in HS-affected areas) for dermatological use	Used within 14 days of the Baseline Visit. Note: Topical steroids in non-HS affected areas are permitted.
Herbal medications for HS	Used within 14 days of the Baseline Visit
Vaccines	Administration of live (including attenuated) vaccines is not allowed within 8 weeks prior to Baseline, during the conduct of the study, and for 20 weeks after the final dose of IMP (see Exclusion Criteria #23 and #24). Administration of inactivated vaccines is allowed during the study at the discretion of the Investigator. Administration of any other vaccine not mentioned above may be allowed following discussion with the Medical Monitor.
Analgesics	See Section 6.5.1.
Spironolactone	Permitted if indicated for non-HS-related condition (eg, polycystic ovary syndrome); and if study participant meets all other entry criteria. Study participant must be on a stable dose for at least 28 days prior to the Baseline visit.

**Table 6–3: Exclusions for prior medications**

Drug class	Exclusion criteria
Metformin	Permitted if indicated for non-HS-related condition (eg, diabetes mellitus); and if study participant meets all other entry criteria. Study participant must be on a stable dose for at least 28 days prior to the Baseline visit.
Finasteride and other 5 $\alpha$ -reductase inhibitors	Permitted if indicated for non-HS-related condition (eg, benign prostatic hypertrophy); and if study participant meets all other entry criteria. Study participant must be on a stable dose for at least 28 days prior to the Baseline visit.

HS=hidradenitis suppurativa; IL=interleukin; IMP=investigational medicinal product

### **6.5.3      Rescue medication**

The Sponsor will not supply rescue medication. The following rescue medications may be used:

#### **6.5.3.1      Antibiotic Rescue Medication/Antibiotics**

Any systemic antibiotic that is initiated (new antibiotic or change in the dose/type of current antibiotic) on or after Baseline (first day of study drug administration) will be considered rescue medication for both the Initial Treatment Period and Maintenance Treatment Period. If a newly initiated systemic antibiotic (or increase in dose/type of antibiotic) is required during the Initial Treatment Period based on disease flare or other extenuating circumstances, the Investigator should discuss the decision with the Medical Monitor.

#### **6.5.3.2      Rescue Medications/Lesion Intervention**

There are no absolute restrictions on the use of rescue medications for study participants whose HS deteriorates during the study. While the objectives of the study should be protected as much as possible through observance of the restrictions detailed above in Section 6.5, the well-being of the study participant will always take priority; study participants should be managed as deemed appropriate by the Investigator.

In the event an acutely painful lesion occurs that requires an immediate intervention, Investigators will have the option to perform interventions. Interventions can include analgesics for a limited period of time (see below), intralesional injections of triamcinolone, and/or incision and drainage of the abscess. Intralesional injections of triamcinolone (up to 20mg across all lesions at a given visit, and using a concentration of no more than 20mg/mL [suspension for injection]) must be consistent with the maximum number of interventions described below and clinical practice. Concomitant use of wound care dressings is permitted; however, options are limited to alginates, hydrocolloids, and hydrogels. Concomitant medications associated with the lesion intervention(s) must be captured in source documents and on the appropriate eCRF.

Any analgesic that is initiated (new analgesic, new class of analgesic, increased dose of an analgesic stable since Baseline, regardless of duration of treatment) after Baseline (first day of study drug administration) will be considered rescue pain medication for the Initial Treatment Period and Maintenance Treatment Period (Weeks 0 to 48).

A total of 2 protocol-allowed interventions are permissible during the Initial Treatment Period (from Baseline Visit to Week 16). Do not include analgesic rescue treatment in the number of protocol-allowed interventions. An intervention can occur on maximally 2 different lesions at the same visit, or on the same lesion at 2 different study visits. The same lesion cannot be treated 2 times at the same visit. If a study participant requires more than 2 interventions within the first 16 weeks of the study, then the study participant should be discontinued from the study.

During the Maintenance Treatment Period (Weeks 16 to 48), a maximum of 2 interventions every 4 weeks are permitted. Do not include analgesic rescue treatment in the number of protocol-allowed interventions. An intervention can occur on 2 different lesions at the same visit or on the same lesion at 2 different study visits. Within each 4-week period, the same type of intervention cannot be used 2 times on the same lesion. If a study participant requires more than 2 interventions within a 4-week period, or has 2 of the same interventions on the same lesion within that period, then the study participant should be discontinued from the study.

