## 7.2 Participant discontinuation/withdrawal from the study

Note: For female study participants, please see Section 8.3.5 for pregnancy that occurs during the study as evidenced by a positive pregnancy test.

Study participants are free to withdraw from the study at any time, without prejudice to their continued care.

A study participant may withdraw from the study at any time at his or her own request, or may be withdrawn at any time at the discretion of the Investigator for safety, behavioral, compliance, or administrative reasons.

If the study participant withdraws consent for disclosure of future information, the Sponsor may retain and continue to use any data collected before such a withdrawal of consent.

If a study participant withdraws from the study, he or she may request destruction of any samples taken and not tested, and the Investigator must document this in the site study records.

See the Schedule of Activities (Table 1-1) for data to be collected at the time of study discontinuation and follow-up and for any further evaluations that need to be completed.

If a study participant does not achieve a partial response (defined as a  $\geq 25\%$  reduction in AN count from Baseline [Week 0]) at any visit from Week 32 to 46, the Investigator should contact the Medical Monitor to discuss whether the study participant should continue on study.

Study participants will be withdrawn from the study, after being encouraged to complete the Premature End of Treatment (PEOT) and the SFU Visit if either of the following events occur:

1. Study participant withdraws his or her consent.
2. The Sponsor or a regulatory agency requests withdrawal of the study participant.

Study participants should be withdrawn from IMP and encouraged by the Investigator to return for all scheduled visits through Week 48, and the SFU Visit (if the Week 48 Visit is  $\geq 20$  weeks after the final dose of IMP, the SFU Visit is not required) if any of the following events occur:

1. Study participant develops an illness that would interfere with his or her continued participation.
2. Study participant is noncompliant with the study procedures or medications in the opinion of the Investigator.

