3. Study participant takes prohibited concomitant medications as defined in this protocol (Section 6.5.2) that may present a risk to the safety of the participant or the integrity of the study data, in the opinion of the Investigator and/or the Medical Monitor and/or UCB study physician.

4. Study participant requires more than the number of protocol-allowed lesion interventions (see Section 6.5.3.2).
5. Study participant has a clinical laboratory value meeting any of the following criteria:
  - a. Hepatotoxicity as described in Section 7.1.2.
  - b. A laboratory value meeting any of the following criteria:
    - Absolute neutrophil count  $<1.0 \times 10^3/\mu\text{L}$
    - Absolute lymphocyte count  $<200 \text{ cells}/\mu\text{L}$

Study participants may remain on IMP if the result is transient. A retest is required within 1 to 2 weeks at a scheduled or unscheduled visit. If the repeat absolute neutrophil count or absolute lymphocyte count is still below the allowable values, the participant must be discontinued from the IMP. If the repeat absolute neutrophil count or absolute lymphocyte count is above the allowable values, the participant may continue to receive IMP.

6. There is confirmation of a pregnancy during the study, as evidenced by a positive pregnancy test (see Section 8.3.5 for more information regarding pregnancies).
7. A study participant considered as having either a suspected new LTBI or who develops active TB or an NTM infection during the study (including but not limited to, conversion demonstrated by interferon gamma release assay [IGRA] or other diagnostic means) must be immediately discontinued from IMP.
  - The study participant must immediately be permanently withdrawn from the study if further examinations result in a diagnosis of the following:
    - active TB or
    - an NTM infection, or
    - latent TB infection and study participant does not initiate TB prophylactic therapy, prematurely discontinues TB prophylactic therapy, or, in the opinion of the Investigator or Sponsor, is noncompliant with TB prophylactic therapy.

The PEOT Visit must be scheduled as soon as possible, but not later than the next regular visit.

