- If the study participant is diagnosed with LTBI during the study and desires to continue in the study, he or she must immediately discontinue IMP and start TB prophylactic therapy. After at least 4 weeks of TB prophylaxis, the IMP can be restarted after discussion with the UCB study physician regarding results of laboratory assessments, physical examination, and TB questionnaire. The full course of TB prophylaxis treatment will be completed during the study.

Confirmed active TB is an SAE and must be captured on an SAE Report Form and provided to the Sponsor in accordance with SAE reporting requirements. As with all SAEs, periodic follow-up reports should be completed as per protocol requirements until such time as the TB infection resolves.

Additional information on TB policies is provided in Section 8.2.6.

8. Study participants with newly diagnosed IBD or with IBD flares during the study must:

- Be referred, as appropriate, to a healthcare professional treating IBD, such as a gastroenterologist
- Discontinue IMP and be followed-up until resolution of active IBD symptoms

If IBD flares increase in severity or frequency during the study, the Investigator should use clinical judgement in deciding whether the study participant should continue on IMP and contact the Medical Monitor and UCB study physician to confirm the study participant's suitability for continued participation in the study.

9. Study participants must be referred immediately to a mental healthcare professional and may be withdrawn from the study based upon the Investigator's judgment of benefit/risk for:

- Active suicidal ideation as indicated by a positive response ("Yes") to Question 4 of the "Since Last Visit" version of the eC-SSRS
- Moderately severe major depression as indicated by a PHQ-9 score of 15 to 19 if this represents an increase of at least 3 points compared to the last visit

The mental health consultation must be recorded in the study participant's source documentation.

10. Study participants must be referred immediately to a mental healthcare professional and must be withdrawn from the study in case of:

- Active suicidal ideation as indicated by a positive response ("Yes") to Question 5 of the "Since Last Visit" version of the eC-SSRS.
- Any suicidal behavior since last visit.
- Severe major depression as indicated by a PHQ-9 score  $\geq 20$ .

The mental health consultation must be recorded in the study participant's source documentation.

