Investigators should contact the Medical Monitor in advance, whenever possible, to discuss the withdrawal of a study participant from IMP or from the study.

Study participants withdrawing from the study who are not continuing for all scheduled visits through Week 48, will undergo the PEOT Visit and the SFU Visit 20 weeks after their final dose of IMP, as applicable.

The eCRF must document the primary reason for withdrawal or discontinuation.

Investigators should contact the Medical Monitor and/or UCB study physician, whenever possible, to discuss the withdrawal of a study participant in advance.

Withdrawn participants will not be replaced.

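### A participant over the lesion-intervention limit leaves the study under Section 6.5.3.2 but only stops IMP under Section 7.2 item 4, and no text says which applies

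*Protocol*

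**What the plan says.** Protocol Section 6.5.3.2 caps lesion interventions at 2 in Weeks 0 to 16 and at 2 per 4 weeks in Maintenance. For the Initial Treatment Period, a participant who "requires more than 2 interventions within the first 16 weeks of the study, then the study participant should be discontinued from the study". In Maintenance the same outcome follows when the 4-weekly limit is exceeded. It also applies to anyone who "has 2 of the same interventions on the same lesion within that period, then the study participant should be discontinued from the study".

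Section 7.2 has two lists:

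- **Study withdrawal.** The lead-in is "Study participants will be withdrawn from the study, after being encouraged to complete the Premature End of Treatment (PEOT) and the SFU Visit". It has two events: withdrawn consent, and a request by the Sponsor or a regulatory agency.
- **IMP withdrawal.** The lead-in is "Study participants should be withdrawn from IMP and encouraged by the Investigator to return for all scheduled visits through Week 48". Item 4 of this list is "Study participant requires more than the number of protocol-allowed lesion interventions", with a cross-reference to 6.5.3.2.

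Where an item on the IMP list also requires leaving the study, the text says so. Item 7 (tuberculosis) has "The study participant must immediately be permanently withdrawn from the study if further examinations result in a diagnosis of the following" and item 10 (suicidality, severe depression) has "Study participants must be referred immediately to a mental healthcare professional and must be withdrawn from the study in case of". Item 4 has no such sentence.

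**The concern.** One event leads to two different outcomes, depending on which section the site reads. The only cross-reference runs from 7.2 to 6.5.3.2, so a reader who follows it from item 4 arrives at the stricter instruction. Section 6.5.3.2 does not point back.

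The second Maintenance trigger (the same intervention twice on the same lesion) is not clearly covered by item 4, which speaks only of the number of interventions. For that trigger, 6.5.3.2 may be the only explicit instruction.

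A participant who passes the limit probably has poorly controlled lesions, so data lost by ending participation are probably informative. Three uses of the data are exposed, to different degrees:

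- **Treatment-policy analysis (9.6 item 3).** It uses Week 16 data whether or not treatment stopped, and states that efforts will be made to obtain them. This is the main effect at Week 16.
- **Primary analysis (9.3.1).** The effect here is narrow and is traced in the working.
- **Maintenance.** Section 4.2 says this period is meant to show durability of response and longer-term safety. Visits to Week 48 would be lost.

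**Working it through.** The contradiction is textual, so the first step compares the instructions. The arithmetic only bounds the loss per participant.

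**1. The instructions compared**

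| Event | Section 6.5.3.2 | Section 7.2 |
|---|---|---|
| More than 2 interventions, Weeks 0 to 16 | Leaves the study | Item 4: stops IMP, visits encouraged to Week 48 |
| More than 2 in 4 weeks, Maintenance | Leaves the study | Item 4: same |
| Same intervention twice on the same lesion in 4 weeks, Maintenance | Leaves the study | Not clearly covered |

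The closing text of 7.2 does not decide between them. It asks for contact with the Medical Monitor where possible and adds "Study participants withdrawing from the study who are not continuing for all scheduled visits through Week 48, will undergo the PEOT Visit"; safety follow-up is also required of them. That describes what leavers receive, not who should leave.

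**2. Effect on the Week 16 outcome**

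Lesion intervention is not an intercurrent event in 9.3.1. Those events are systemic antibiotic rescue, and stopping treatment for an AE or lack of efficacy.

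- If rescue antibiotic was used, or the stop was coded as AE or lack of efficacy, the composite outcome is non-response under either reading.
- If neither applies, the 6.5.3.2 reading leaves Week 16 missing, and it is multiply imputed under missing at random (9.3.1, 9.6). Under the 7.2 reading it can be observed.
- In the treatment-policy analysis, the 6.5.3.2 reading replaces a potentially observed Week 16 value with an imputed one in all of these cases.

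**3. Maximum loss per participant after Week 16**

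- Visits every 2 weeks, Weeks 18 to 48 (4.1): (48 − 18)/2 + 1 = 16.
- Lesion counts (Table 1-1, row matched to its column headings): Weeks 20, 24, 28, 32, 36, 40, 44 and 48 = 8.
- A participant removed before Week 16 also loses the Week 16 count. Leavers who do not continue visits have one PEOT lesion count and an SFU Visit instead.

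**4. What a wording change could still protect**

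Section 9.8 says the pain-response endpoint was added after randomization was complete. Amendment 4, dated 09 May 2022, added it, so that date is the latest possible for the last randomization.

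- Last Week 16: 09 May 2022 + 112 days = 29 Aug 2022 (visit window ±3 days).
- Last Week 48: 09 May 2022 + 336 days = 10 Apr 2023 (visit window ±3 days).
- Amendment 5 is dated 27 Sep 2022, which is 141 days after 09 May 2022; 141/7 = 20.1 weeks.
- Visits left after Week 20.1: Weeks 22 to 48, (48 − 22)/2 + 1 = 14.
- Lesion counts left: Weeks 24 to 48 every 4 weeks, (48 − 24)/4 + 1 = 7.

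The Protocol gives no rate of exceeding the limit, so the effect on any analysis cannot be calculated.

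**The case against.** The best defence is that 6.5.3.2 is loosely worded and the rest of the Protocol shows what is meant. Section 7.1 sets a general rule of continued visits after IMP is stopped, 7.2 item 4 applies it to this event, and 9.6 item 3 commits to collecting Week 16 data. Section 7 is also the part devoted to discontinuation.

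The terminology is imprecise elsewhere too. Section 8.2.6.3.5 moves from immediate withdrawal to withdrawal from study treatment within one paragraph. Section 8.3.5 withdraws a pregnant participant from the study, while Appendix 4 allows either outcome. The two-event study-withdrawal list is not exhaustive, since items 7 and 10 add to it.

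This shows which reading was probably intended. It does not make 6.5.3.2 safe to follow as written, because the instruction appears there for both periods and nothing overrides it. Contact with the Medical Monitor may resolve single cases but is not a rule.

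Other parts of the objection stand:

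- The same-lesion trigger can be read into item 4: the same type is allowed only once per lesion in 4 weeks, so twice exceeds the number. The gap is arguable.
- Maintenance endpoints are not formally tested, and attendance under 7.2 is only encouraged.
- The figures of 14 visits and 7 counts are a ceiling. They assume the change takes effect on the Amendment 5 date and describe the last participant randomized; others had no more left to save.
- The listing goes beyond the wording defect. The primary reason for withdrawal is already recorded in the eCRF, and such tabulations are often left to the SAP.

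**Conclusion.** The concern holds and is minor. Sections 6.5.3.2 and 7.2 item 4 give different outcomes for exceeding the limit, in both treatment periods, and nothing reconciles them. Sections 7.1, 7.2 and 9.6 item 3 all favour continued follow-up, so 6.5.3.2 is the text that is wrong.

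The size is known only as the per-participant ceiling: 16 visits and 8 lesion counts after Week 16, plus the Week 16 count for earlier removals. That the lost data are informative is a judgement about who exceeds the limit; the Protocol gives no figure for it. Following 7.2 would reduce the loss but not remove it.

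**What to change.** 1. In both the Initial and Maintenance paragraphs of 6.5.3.2, replace the instruction to leave the study with withdrawal from IMP and continued visits to Week 48 and the SFU Visit, citing Section 7.2.
2. Extend 7.2 item 4 to cover, in Maintenance, the same intervention given twice on the same lesion within 4 weeks.
3. Before unblinding, list the participants who left the study at the limit and whether each has a Week 16 lesion count. Report the number by arm after unblinding.

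The cost is two phrases, one clause and one blinded listing, with no extra participants and no visits beyond those 7.2 already schedules. At Amendment 5 the wording could protect Maintenance visits only, because Week 16 had passed for everyone; the listing covers that period. It can be made while blinded, since 9.7.2 places the unblinded analysis after the last participant has completed Week 48 or discontinued earlier.
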